proximal of the bifurcation into posterior descending artery and right postero-lateral branch; (4) middle of the left main (LM); (5) proximal left anterior descending artery (LAD) 1.0 cm after LM bifurcation or, if less distance to the 1st diagonal branch, in the middle of the proximal LAD; (6) mid LAD 2.0 cm distal of 1st diagonal branch or if less distance to the 2nd diagonal branch, in the middle of mid LAD; and (7) left circumflex coronary artery 2.0 cm distal of the LM bifurcation. Positions were located in the non-contrast images and reaffirmed on CCTA images using a corresponding phase of the cardiac cycle. Locations with non-calcified or calcified plagues or unclear depiction of the coronary artery due to adjacent structures such as veins were avoided, and in those segments, the location of measurement was moved distally up to 1.0 cm from the original position while staying in the same coronary segment and avoiding bifurcations. If coronary diameters could not be measured at any of these positions, the location was excluded. We excluded stented or bypassed locations from measurements. All coronary diameters were measured twice at each location using short-axis views in an enlarged field-of-view and averaged using window width and level of 350 HU and 50 HU for non-contrast and 800 HU and 200 HU for CCTA images (Figure 2). Window settings were set based on preliminary measurements in 20 patients who underwent CCTA without nitroglycerin and therefore no diameter differences in non-contrast and CCTA images. Locations #1, #4, and #5 were defined as proximal-, locations #2 #6, and #7 as mid-, and location #3 as distal coronary segments.

Safety

By query, side effects were evaluated, including headache, dizziness, and nausea during the exam. The severity of headache was quantified on a 10-point scale ranging from 1 minimal- to 10 maximal-intensity.

Statistical Analysis

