Demographic and scan parameter summaries were calculated for the entire subject cohort and by nitroglycerin administration method. Categorical variables were summarized using frequencies and percentages, while continuous variables were summarized as means and standard deviations, or as median and interquartile range (25^{th} and 75^{th} percentiles) if the distribution of the variables were skewed. Differences in continuous variables by treatment were assessed using the Kruskal-Wallis test, and differences in categorical variables were assessed using either the Pearson χ^2 test, or Fisher's exact test. Changes of vital parameters pre- and posttreatment were compared using paired t-test.

A linear quantile (median) mixed-effects model was constructed to quantify the unadjusted association between treatment and vasodilation (contrast diameter/non-contrast diameter x 100) while accounting for dependencies within the data set due to multiple observations per subject. This modeling approach permitted the estimation of the median vasodilation as a function of covariates while avoiding the parametric modeling assumptions that are typically associated with linear mixed models. Estimates of fixed-effects, and their 95% Wald-type confidence intervals, were computed for all model

parameters. Linear combinations of these parameters were used to estimate overall effects, and effects by treatment.

Two additional models were constructed where we hierarchically accounted for patient demographics (i.e., age, gender, BMI and height) and then by patient demographics and disease severity measure (i.e., CA score). A subgroup analysis was performed where model parameters were estimated by proximal, mid and distal regions. Due to the explorative nature of this subgroup analysis, p-values were not adjusted for multiple comparisons.

All analyses were performed using R 3.4.3 (R-Core Team, 2017, Vienna, Austria) (20) and the lqmm R library (21).

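### The exploratory regional analysis gives arm differences within regions of 3, 3 and 1 locations but describes no treatment-by-region contrast, so it cannot show whether the arm difference varies by region

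*Combined protocol and SAP*

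**What the plan says.** Under Quantitative Analysis, the seven measurement locations are grouped in advance: "Locations #1, #4, and #5 were defined as proximal-, locations #2 #6, and #7 as mid-, and location #3 as distal coronary segments". That makes 3 proximal, 3 mid and 1 distal location per patient.

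Under Statistical Analysis, the main model is a median mixed-effects model of treatment on vasodilation, "accounting for dependencies within the data set due to multiple observations per subject". Wald 95% intervals are planned for its parameters. The contrasts are described in one sentence: "Linear combinations of these parameters were used to estimate overall effects, and effects by treatment". The regional analysis follows: "A subgroup analysis was performed where model parameters were estimated by proximal, mid and distal regions". On its status the plan says: "Due to the explorative nature of this subgroup analysis, p-values were not adjusted for multiple comparisons".

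No treatment-by-region term, interaction test or interval for a between-region difference in the arm effect is described. Whether the regions are fitted jointly or separately is not stated.

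**The concern.** Splitting results by region invites the question of whether the delivery methods differ more in some parts of the coronary tree than in others. The plan's outputs do not answer it. Each regional estimate, interval and p-value addresses the arm difference inside one region. Setting the three p-values side by side is not a test of variation, for two reasons:

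- The distal region has a third of the observations per patient that the other two have, so its power is lower by design.
- The three estimates come from the same patients and are correlated, so their separate standard errors do not give the standard error of a difference between them.

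At stake is the reading of an exploratory result. A pattern such as a significant difference proximally and none distally is common when the arms differ equally everywhere, and could be reported as a regional effect.

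**Working it through.** **Inputs from the documents.** 66 patients per arm and 198 in total (Methods; 3 × 66 = 198). Regions of 3, 3 and 1 locations (Quantitative Analysis), so at most 198 × 3 = 594, 594 and 198 rows, or 1,386 in all. No power or sample size is stated for the regional analysis, so there is no plan figure to reproduce.

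**Assumptions.** The documents give no SD. I take patient SD 4 and residual SD 7 percentage points; the ranges below also cover the pairs (3, 5), (6, 10) and (3, 9). One pair of arms, two-sided 0.05, no lost locations, and the same true arm difference in every region.

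**Step 1: analytic standard errors, mean scale.** For a region of k locations, SE = sqrt((2/66) × (patient variance + residual variance / k)).

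- Proximal or mid: sqrt((2/66) × (16 + 49/3)) = 0.99.
- Distal: sqrt((2/66) × (16 + 49)) = 1.40.
- Distal minus proximal: the patient effect cancels, leaving sqrt((2/66) × 49 × (1 + 1/3)) = 1.41.
- The same difference with the shared patients ignored: sqrt(0.99² + 1.40²) = 1.71.

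**Step 2: median scale, by simulation.** There were 8,000 two-arm trials per SD pair. The regional contrast is the difference of pooled regional medians, which approximates the planned quantile mixed model but is not that fit. The SEs are 1.17 (proximal), 1.17 (mid) and 1.73 (distal). Distal minus proximal has SE 1.84, against sqrt(1.17² + 1.73²) = 2.09 without the covariance.

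**Step 3: power within each region at a common 3-point difference.** Power is about Φ(3/SE − 1.96).

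- Proximal and mid: Φ(2.56 − 1.96) = 73%.
- Distal: Φ(1.73 − 1.96) = 41% (40% in the simulation).

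**Step 4: how often the three p-values fall on both sides of 0.05** (median scale, SDs 4 and 7).

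| Same true difference in all regions (points) | Trials with disagreement |
|---|---|
| 0 | about 14% |
| 1 | about 28% |
| 2 | about 57% |
| 3 | about 64% |
| 4 | about 43% |

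At 3 points the other SD pairs give 38% to 73%. On the mean scale the 3-point figure is 47% (18% to 64%). The pattern of proximal significant and distal not occurs in about 41% of trials at 3 points (30% to 44% over the SD pairs). A joint interaction test rejects in 5%. That is its nominal level by construction and is shown only for contrast.

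**Step 5: how much of this comes from the 3/3/1 split.** At 3 points, proximal and mid, which are equal in size, still disagree with each other in about 30% of trials. A good part of the 64% is therefore what any set of subgroup p-values would show.

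**Step 6: what a between-region contrast can detect.** Detectable difference at 80% power = 2.802 × SE = 2.802 × 1.84 = 5.2 points for distal minus proximal (3.7 to 7.5 over the SD pairs). At a true regional difference of 3 points, power is Φ(3/1.84 − 1.96) = Φ(−0.33), about 37%.

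**The case against.** The strongest reply is that the plan never says regional p-values will be compared. It calls the analysis exploratory and asks only for parameters by region. That stands. A reader might infer that the authors intend to claim effect modification from disagreeing p-values, but the documents do not support this. The point is a missing estimate, not a declared wrong inference. The exploratory label does not fill the gap, because the plan uses it to justify leaving multiplicity unadjusted, and adjusted p-values would not compare regions either.

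The planned 95% intervals are a real safeguard. If they carry over to the regional fits, a reader will see how wide the distal interval is. They still do not give an interval for the difference between regions.

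The regional fit might already be joint, and the sentence on linear combinations comes before the subgroup sentence, so it is weak evidence about the subgroup. That is fair: the absence is of a described term or contrast, not proof that none was fitted. If the fits are separate, resampling patients across the three fits would recover the covariance. Ignoring it errs on the cautious side, by about 14% in the standard error (2.09 against 1.84).

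The disagreement rate depends on the assumed difference and SDs, and 3 points is close to its maximum. The full range from 0 to 4 points is therefore given above.

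**Conclusion.** The point holds as a cheap, optional improvement to an exploratory analysis. As described, the regional analysis can show an arm difference within a region but not whether that difference varies between regions. Under the assumed SDs, disagreeing regional p-values would appear in roughly 14% to 64% of trials with no regional variation at all, depending on the common true difference. The exact rates rest on assumed SDs, complete location data and an approximation to the planned estimator. Across the SD pairs and both scales, distal always has the lowest power at a common non-zero difference.

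Two stronger readings should be resisted. The first is that the regional p-values are invalid; each remains a test of the arm difference in its own region. The second is that the primary result is compromised, for instance because locations can be excluded ("If coronary diameters could not be measured at any of these positions, the location was excluded"; "We excluded stented or bypassed locations from measurements") while no model names location. Randomization balances stent, bypass and plaque exclusions on average, and the documents do not show unequal loss between arms. Nothing here calls for a change to the primary model or the pooled contrast.

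**What to change.** For the exploratory analysis only:

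1. Fit one median mixed model over all locations with treatment, region and treatment-by-region terms and a patient random intercept. With three arms and three regions there are (3 − 1) × (3 − 1) = 4 interaction terms.
2. Report the arm differences within each region and the between-region differences in those arm differences, all with 95% intervals, together with the interaction test.
3. State that regional p-values are not compared with each other.

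The cost is a few sentences in the SAP and a handful of extra parameters in up to 1,386 rows; no new data are needed. There are two downsides. The joint model assumes common scatter across regions. The interaction test is also weak: with a detectable distal-minus-proximal difference of about 5 points, the report should say that a non-significant interaction does not show equal effects, and should lead with the intervals.
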